APPENDIX D: PTQA Email Example

Dear Dr. [Provider name],

Please see the attached reports for QOL changes pre/post transfusion for the patients below. I'll also send the patients these reports.

[Pt Initials] (MRN) – Index transfusion on [Date]

- This participant's score increased from 80 to 90 points, indicating a clinically significant increase in QOL.
- Per the study, we do not recommend any change in transfusion plan at this time.

[Pt Initials] (MRN) – Index transfusion on [Date]

- This participant's score remained stable at 39 points, indicating no clinically significant changes in QOL.
- Per the study, we suggest that she may consider limiting the number of transfusions she receives, given no end-organ effects of anemia and if her Hb stays above 7.5 g/dL

PROTOCOL TITLE: A New Paradigm of Transfusion Decision Support for Patients with MDS:

Using Peri-Transfusion Quality of Life Assessments (PTQAs)

APPENDIX E: TWO-MONTH FOLLOW UP SURVEY

Initials: _____

Study ID: _____

Date: _____

PTQA UTILIZATION

Please think back to the PTQA results report you received after your post-transfusion questionnaire.

1. Did you and your doctor discuss the results of your PTQA report?
 - a. Yes
 - b. No

If yes...

2. Who initiated the PTQA/quality of life discussion?
 - a. I did
 - b. My doctor did
3. Did the results of the report affect your or your doctor's decision to pursue future transfusions?
 - a. Yes
 - b. No

DECISION REGRET SCALE

Please think about the decision you made about future blood transfusions after talking to your doctor. Please show how you feel about these statements by circling a number from 1 (strongly agree) to 5 (strongly disagree).

	1 Strongly Agree	2 Agree	3 Neither Agree Nor Disagree	4 Disagree	5 Strongly Disagree
4. It was the right decision					
5. I regret the choice that was made	1 Strongly Agree	2 Agree	3 Neither Agree Nor Disagree	4 Disagree	5 Strongly Disagree
6. I would go for the same choice if I had to do it over again	1 Strongly Agree	2 Agree	3 Neither Agree Nor Disagree	4 Disagree	5 Strongly Disagree
7. The choice did me a lot of harm	1 Strongly Agree	2 Agree	3 Neither Agree Nor Disagree	4 Disagree	5 Strongly Disagree
8. The decision was a wise one	1 Strongly Agree	2 Agree	3 Neither Agree Nor Disagree	4 Disagree	5 Strongly Disagree

[figure not shown]
ABOUT YOUR CANCER CARE

PROTOCOL TITLE: A New Paradigm of Transfusion Decision Support for Patients with MDS:
Using Peri-Transfusion Quality of Life Assessments (PTQAs)

These questions ask about your outpatient cancer care during the past twelve months; remember that you can leave any questions blank if you are not comfortable answering. When answering, please do not include care you got when you stayed overnight in a hospital.

[figure not shown]
9. Using any number from 0 to 10, where 0 is the worst possible and 10 is the best possible, what number would you use to rate your cancer care overall?

10. In the last 12 months, when you needed care right away from your cancer doctor for a new symptom or condition, how often was your concern addressed as soon as you wanted?

- 1 Never
- 2 Sometimes
- 3 Usually
- 4 Always
- 5 Not applicable, never needed care right away

11. Using any number from 0 to 10, where 0 is the worst possible and 10 is the best possible, what number would you use to rate the doctor who prescribes your chemotherapy or hormonal therapy?

12. In the last 12 months, how often did your cancer doctors, nurses or other cancer providers spend enough time with you?

- 1 Never
- 2 Sometimes
- 3 Usually
- 4 Always

13. In the last 12 months, how often did your cancer doctors, nurses or other cancer providers explain things in a way you could understand?

- 1 Never
- 2 Sometimes
- 3 Usually
- 4 Always

**PROTOCOL TITLE: A New Paradigm of Transfusion Decision Support for Patients with MDS:
Using Peri-Transfusion Quality of Life Assessments (PTQAs)**

14. The role patients would like to play in making treatment decisions about their cancer may sometimes differ from how decisions actually get made. Which statement best describes the role you would prefer to play when decisions about treatment for your cancer are made?

- 1 I prefer to make decisions about my treatment with little/no input from my doctors
- 2 I prefer to make the decisions after considering my doctor's opinion
- 3 I prefer that my doctors and I make the decisions together
- 4 I prefer that my doctors make the decisions after considering my opinion
- 5 I prefer my doctors make the decisions with little or no input from me

PERCEIVED STRESS

15. The following questions ask you about your feelings and thoughts during the last month. In the last month, how often have you felt ...

	Never					Often
...that you were unable to control the important things in your life?	1	2	3	4	5	
...confident about your ability to handle your personal problems?	1	2	3	4	5	
...that things were going your way?	1	2	3	4	5	
...difficulties were piling up so high that you could not overcome them?	1	2	3	4	5	

**PROTOCOL TITLE: A New Paradigm of Transfusion Decision Support for Patients with MDS:
Using Peri-Transfusion Quality of Life Assessments (PTQAs)**

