7. Participants will be instructed to complete this survey exactly one week after transfusion and return it using the pre-addressed, pre-stamped envelope.
8. Site RAs will call participants using script (see Appendix D) to remind them to complete the QUALMS survey exactly one week after transfusion.
 - The window may increase up to one extra week to accommodate for circumstances where the patient is unable to complete the post-transfusion QUALMS (i.e., participant does not feel well or participant forgot).

PTQA Report

9. Once received, the second assessment will be scored and compared with the first, and both the patient and provider will be sent a report with the results. The QUALMS validation study suggested that a clinically meaningful difference on the instrument is between 5 and 10 points;¹² For this study:
 - A post-transfusion score that is within 5 points of the pre-transfusion score will indicate a stable QOL
 - A post-transfusion score that increases by 5 or more points will indicate a clinically significant improvement in QOL
 - A post-transfusion score that decreases by 5 or more points will indicate a clinically significant decline in QOL
10. In our report, we will include language that encourages patient and providers to use these results to inform their next transfusion decision, specifically suggesting that transfusion be halted or decreased in frequency if QOL has worsened.

**PROTOCOL TITLE: A New Paradigm of Transfusion Decision Support for Patients with MDS:
Using Peri-Transfusion Quality of Life Assessments (PTQAs)**

Secondary Outcomes Assessment

11. At 8 weeks post-transfusion, all participants will be sent a survey (Appendix B) to assess the utilization of the PTQA and patients' decisional regret, perceptions of care, and perceived stress.

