We may find that patients and hematologists do not use the information in their PTQA reports to truly affect decision-making, as both may be anxious to forgo transfusions despite the fact that QOL did not improve. We plan to assess this parameter at two months post-transfusion by asking participants whether they discussed the PTQA report with their physician (see Appendix B). To help prevent the PTQA going unused, we will make sure that providers at each site have access to the consensus Hb data from our previous qualitative study (Protocol 18-064). These results will be disseminated to providers prior to study initiation. In addition, we will work closely with the DFCI Adult Patient and Family Advisory Council (PFAC) to vet the routine language in our PTQA patient reports so that is optimally educational and anxiety-reducing.

PROTOCOL TITLE: A New Paradigm of Transfusion Decision Support for Patients with MDS: Using Peri-Transfusion Quality of Life Assessments (PTQAs)

Exploratory analyses (e.g. descriptive statistics such as means and standard deviations) using the results from the follow-up survey (see Appendix B) will characterize decisional regret, perceptions of care, and perceived stress by the associated scales at two months post-transfusion (Table).

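### The two-month survey records an effect of the PTQA report on transfusion decisions only after a reported discussion, and without direction

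*Protocol*

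**What the plan says.** PTQA utilization is one of four outcomes under Specific Aim 3 (section 1.1). Section 11.1 explains why it matters: "We may find that patients and hematologists do not use the information in their PTQA reports to truly affect decision-making". The same paragraph names the measure: "We plan to assess this parameter at two months post-transfusion by asking participants whether they discussed the PTQA report with their physician".

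The instrument is printed in Appendix E (the body text cites it as Appendix B). Item 1 is "Did you and your doctor discuss the results of your PTQA report", answered Yes or No. An if-yes line follows, then item 2 (who raised the subject) and item 3, "Did the results of the report affect your or your doctor's decision to pursue future transfusions", again Yes or No. No route is given for a No to item 1. The Decision Regret Scale comes next, with the stem "Please think about the decision you made about future blood transfusions after talking to your doctor" and no not-applicable choice.

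On who is asked, section 9.2 says: "At 8 weeks post-transfusion, all participants will be sent a survey (Appendix B) to assess the utilization of the PTQA". On who gets the report, it says: "both the patient and provider will be sent a report with the results".

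**The concern.** The question in section 11.1 is whether the report changes decisions, but the measure named is whether a conversation took place. A conversation can leave the plan unchanged, and a plan can change without one. The single item that asks about effect is reached only through the conversation item.

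The hypothesis in section 1.2 has a direction, namely less transfusion. Item 3 has none, so a Yes from a patient who cut back looks the same as a Yes from one whose plan moved the other way or who carried on because of the report.

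Aim 2 compares participants with historical controls from 2015 to 2017. The survey is the only place where participants are asked whether the report itself influenced a decision. The form is fixed in the protocol, and no later analysis can recover an answer that was never collected.

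**Working it through.** The protocol states no expected rate, sample size or power for this outcome, so there is no figure to reproduce. The check compares the parts of the protocol and then bounds what the skip leaves unknown.

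**1. Target against measure.** Section 11.1 is concerned with effect on decision-making. Its stated measure is discussion, which is item 1. Item 3 does ask about effect, but 11.1 does not mention it.

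**2. Who reaches item 3.** The if-yes line stands before items 2 and 3, and nothing ends the branch before item 3. On the natural reading, only those who answered Yes to item 1 answer item 3.

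**3. Can an effect arise without a discussion?** Yes. Under section 9.2 the report goes to both parties. In Appendix C, the stable-score and decreased-score reports each tell the patient that limiting transfusions may be considered. The sample email in Appendix D gives the provider a similar suggestion. Either party can act on that alone.

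**4. Direction.** Section 1.2 predicts a decrease. Item 3 offers two answers and cannot show one.

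**5. Bounds.** Let N be the number of report recipients who return the survey, d the number who discussed the report, and y the number of those answering Yes to item 3. Nothing is known about the other N − d, so the share of all N with an affected decision lies between

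- lower bound: y / N
- upper bound: (y + N − d) / N
- width: (N − d) / N

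N = 60 is the evaluable target in section 4.1, with full return assumed. The values of d, and y at half of d, are assumptions.

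| d | y | Lower | Upper | Width |
|---|---|---|---|---|
| 18 | 9 | 9/60 = 15% | 51/60 = 85% | 70 points |
| 30 | 15 | 15/60 = 25% | 45/60 = 75% | 50 points |
| 42 | 21 | 21/60 = 35% | 39/60 = 65% | 30 points |
| 54 | 27 | 27/60 = 45% | 33/60 = 55% | 10 points |

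Changing the assumed Yes rate moves the interval but not its width. With d = 30, y = 9 gives 9/60 = 15% to 39/60 = 65%, and y = 21 gives 21/60 = 35% to 51/60 = 85%. The skip matters when discussion is uncommon and little when nearly everyone discusses the report.

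**6. Regret stem.** It asks about a transfusion decision made after talking to the doctor and does not mention the PTQA report. Section 8.1 describes the construct as regret over transfusion decisions. The stem lacks a referent only for a patient who had no such talk or made no such decision. Elsewhere the forms do give an exit: item 10 of the same survey and QUALMS items 34 to 38 have a not-applicable choice.

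**The case against.** **The skip has a reason.** The reports direct patients to act through a talk with their doctor, and item 3 covers the doctor's decision as well as the patient's. A patient who never discussed the report can hardly say whether it moved the doctor. This stands in part. Asking everyone will not fully capture use by the provider alone, but it does capture the patient's own decision.

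**Direction can be pieced together.** No report template suggests more transfusion, each participant's report category is known, and chart review records later transfusions (section 9.4). This also stands in part. Linkage shows what happened, but not that the respondent credits the report with it.

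**The layout is open to another reading.** The if-yes line might cover item 2 only. That is possible but less natural, and an unclear skip on a self-completed form is itself worth repairing.

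A reader might also infer more than the protocol supports:

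- *That everyone answering No to item 1 gives an invalid regret score.* The stem does not require a talk about the report. A patient who discussed transfusion in general can answer it properly.
- *That patients who skip item 3 are counted as non-users.* The protocol contains no such coding rule.
- *That Aim 3 as a whole, or Aim 2, is compromised.* Perceptions of care and perceived stress are untouched, section 11.1 treats the survey scales as exploratory and descriptive, and the Aim 2 endpoints come from medical records.

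**Conclusion.** The point holds in a limited form. Section 11.1 names discussion as the measure of a question about effect. Appendix E then confines its one effect item to those who discussed the report and gives it no direction. An effect on the patient's decision without a discussion goes unrecorded, and a Yes cannot be tied to the hypothesised decrease.

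The number of patients affected cannot be derived from the protocol. The bounds above rest on assumed discussion and Yes rates and on 60 returned surveys, and they show only how the uncertainty depends on how common discussion is. The regret-scale gap is minor. Two of the four exploratory Aim 3 outcomes are concerned, utilization and regret, and the Aim 2 comparisons and their power are unaffected. The change is still worth making, because it is nearly free and the missing answers cannot be recovered afterwards.

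**What to change.** 1. In Appendix E, take item 3 out of the if-yes branch and put it to every participant who received a report. Limiting it to recipients matters because, under section 11.4, no report is generated when the post-transfusion QUALMS is missing. Offer four answers: fewer or delayed transfusions, no effect, more or earlier transfusions, don't know.
2. In section 11.1, name item 3 as the measure of effect on decisions, and report item 1 (discussion) separately.
3. As a minor addition, put one tick box for no decision made or not applicable ahead of the five regret items, leaving the items unchanged, and report how many tick it. A filter that restricts the regret summary to patients who report a decision since the report would be more debatable. It selects on a response given after the intervention and could drop those who simply continued.

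The cost is a small revision to one form and a sentence in section 11.1, with no added visits. The main downside is that patients may not know whether the report affected the doctor's decision, so some will answer don't know and provider-only use stays partly unmeasured. There may also be slightly fewer regret scores.

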1.0 Objectives

1.1 Study Aims

The goal of this multi-center study is to determine how to tailor blood transfusion decisions to the quality of life (QOL) changes experienced by individual patients with myelodysplastic syndromes (MDS). We will assess this by piloting a peri-transfusion QOL assessment (PTQA) approach. The PTQA involves administering a QOL questionnaire (see Appendix A) to study participants before and after an upcoming transfusion appointment and comparing QOL scores.

Specific Aim 1

Assess the feasibility of PTQA. We will assess the feasibility of this new paradigm of decision support by determining the enrollment yield as a percentage of all patients approached. We will also assess feasibility by calculating the proportion of enrolled participants who complete both the pre- and post-transfusion the Quality of Life in Myelodysplasia Scale (QUALMS).

Specific Aim 2

Assess the potential usefulness of PTQA in improving clinical and utilization outcomes. We will use medical record review and match our participants to historical controls (matched for transfusion group; IPSS-R; pre-transfusion Hb; and institution) to assess our primary outcomes, which are:

1. The presence of second transfusion after PTQA (for transfusion-naive)
2. The number of red cell units used after PTQA (for transfusion-dependent)
3. The number of hospitalizations after PTQA (for both transfusion groups)
4. The number of clinic visits after PTQA (for both transfusion groups)

Specific Aim 3

Explore the potential impact of PTQA on patient-reported outcomes. At 8 weeks post-transfusion, we will send participants a follow-up questionnaire (see Appendix B) to assess the following secondary outcomes:

1. PTQA utilization
2. Decisional regret
3. Perception of care
4. Perceived stress

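### The care-perception block asks at week 8 about the past 12 months, so its answers are dominated by care before PTQA and cannot separate care before from care after it

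*Protocol*

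**What the plan says.** Section 1.1 gives the purpose of Aim 3 as "Explore the potential impact of PTQA on patient-reported outcomes" and lists perception of care among its outcomes. Section 8.1 makes it a secondary endpoint at two months, measured with a six-item domain taken from a prior survey.

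Section 9.2 fixes the timing: "At 8 weeks post-transfusion, all participants will be sent a survey (Appendix B) to assess the utilization of the PTQA". The body cites the survey as Appendix B; it is printed as Appendix E. Section 9.2 also sets when the information for a PTQA report first becomes available: "Participants will be instructed to complete this survey exactly one week after transfusion", with up to one further week allowed.

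The care block is items 9 to 14 of Appendix E:

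- The instruction above the items sets the period: "These questions ask about your outpatient cancer care during the past twelve months".
- Item 10 repeats it: "In the last 12 months, when you needed care right away from your cancer doctor for a new symptom or condition". Item 12 does too: "In the last 12 months, how often did your cancer doctors, nurses or other cancer providers spend enough time with you". Item 13 uses the same opening.
- Items 9 and 11 are ratings from 0 to 10 that state no period of their own, so the instruction governs them. Item 11 asks about "the doctor who prescribes your chemotherapy or hormonal therapy".
- Item 14 asks for a preference and has no recall period in its own wording: "Which statement best describes the role you would prefer to play when decisions about treatment for your cancer are made".

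Section 11.1 plans descriptive summaries of these answers, such as means and standard deviations.

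**The concern.** An outcome meant to explore the effect of PTQA should describe the time after PTQA. A 12-month recall asked at 8 weeks mostly describes the time before it. The recall period is fixed when the patient answers, so no analysis can recover the intended one. The protocol describes no administration of this block before the transfusion, and the historical controls come from medical record review (Section 1.1, Aim 2), so they have no survey answers. A mean care rating could then be reported as bearing on PTQA when it largely reflects months in which the patient had not met the intervention.

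Item 11 raises a separate, smaller matter. Section 3.2 does not require chemotherapy or hormonal therapy, yet the item assumes someone prescribes one of them and, unlike item 10, shows no not-applicable choice.

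**Working it through.** The plan states no figure on this point, so there is none to reproduce.

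**Inputs**

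- Recall period: 12 months, taken as 365 days (Appendix E).
- Survey time: 8 weeks = 56 days after index (Section 9.2), assumed to be answered when sent.
- Earliest point for a PTQA report: day 7, or day 14 if the extra week is used (Section 9.2). Mail return and scoring add to this, by an amount the protocol does not give.

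**Share of recall before the index transfusion**

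- (365 − 56)/365 = 309/365 = 84.7%.
- In weeks: 44/52 = 84.6%.
- If two months is taken as 61 days: 304/365 = 83.3%.

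**Share of recall before the PTQA report**, (365 − (56 − report day))/365

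| Report day | Days after report | Share before report |
|---|---|---|
| 7 | 49 | 316/365 = 86.6% |
| 14 | 42 | 323/365 = 88.5% |
| 21 (assumed) | 35 | 330/365 = 90.4% |
| 28 (assumed) | 28 | 337/365 = 92.3% |

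**Sensitivity to a late reply (assumption).** Answered on day 63 or 70, the share before index is 302/365 = 82.7% or 295/365 = 80.8%. With a reply on day 70 and a report on day 7, the share before the report is (365 − 63)/365 = 82.7%. The conclusion does not change.

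**Share that can carry an effect.** After index: 56/365 = 15.3%. After the report: at most 49/365 = 13.4% (day 7) or 42/365 = 11.5% (day 14). If patients weighted the year evenly, a true change in perceived care would appear at about 12% to 15% of its size.

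**Other instruments in the protocol**

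| Instrument | Reference period | Share before index at week 8 |
|---|---|---|
| PSS-4 (Appendix E, item 15) | last month, about 30 days | 0% |
| Decision regret (items 4–8) | the decision made after talking to the doctor | not a calendar period |
| PTQA utilization (items 1–3) | the PTQA report itself | not a calendar period |
| Care block (items 9–13) | past 12 months | 84.7% |

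The QUALMS, given around the transfusion, limits answers to the past week. The mismatch is confined to the care block.

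**Effect of shorter recall.** Anchored to the transfusion date, 0% of the period precedes index, though 7/56 = 12.5% to 14/56 = 25% still precedes the earliest report. Anchored to receipt of the report, 0% precedes it.

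**The case against.** The protocol asks little of this endpoint. Aim 3 is exploratory, the analysis is descriptive, and no test, power statement or decision rests on it. It is one of four Aim 3 outcomes, and the other three are tied to the report, the decision or the last month. Keeping an existing item set unchanged is a recognised choice, since rewording gives up comparability. Shorter recall also supplies neither a baseline nor a control, so the result would still be a single rating after PTQA.

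Most of this stands, and it limits the weight of the point. It does not remove it: the protocol plans no comparison with earlier uses, and Section 8.1 already tailors the regret scale to transfusion decisions while stating no tailoring for the care block.

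Three stronger readings are tempting, and the documents do not support them:

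- *The endpoint cannot reflect PTQA at all.* Some 12% to 15% of the recall period follows the report or the index transfusion, and patients may give recent care more weight.
- *Any effect is diluted about eightfold.* That needs even weighting over the year, which nothing in the protocol establishes.
- *Many participants have no prescriber of the kind named in item 11.* The protocol gives no such share. The QUALMS item on treatment ceasing to work offers a not-applicable choice for patients not being treated, which shows only that some may be in that position. The block instruction also lets patients leave questions blank.

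**Conclusion.** The point holds as a mismatch between instrument and aim. The 12-month period governs items 9 to 13 but not item 14, and it sits in the instruction and in items 10, 12 and 13, not in the block title. For a survey answered at week 8, about 85% of the recall period precedes the index transfusion and about 87% to 88% or more precedes any PTQA report. The answers are dominated by care before PTQA and, with no baseline administration described, cannot separate it from care after PTQA. These are shares of calendar time; how patients actually weight the period is unknown. The consequence is limited to one secondary, descriptive endpoint, but it is worth correcting because it cannot be repaired once the surveys are returned. Item 11 is a minor wording matter of unknown extent.

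**What to change.** 1. In the block instruction and in items 10, 12 and 13, replace the 12-month period with 'since you received your PTQA report'. The alternative, 'since your transfusion on [date]', is simpler but still takes in the 1 to 2 weeks or more before the report. It is the only usable anchor for participants without a report: Section 9.2 sends the survey to everyone, while Section 11.4 says that no report is produced if the post-transfusion QUALMS is missing.
2. State that the result is a descriptive rating after PTQA, without a comparator. The rewording corrects the period; it does not supply a comparison.
3. Reword item 11 to the doctor managing the patient's MDS, or add a not-applicable choice.
4. Leave item 14 as it is.

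The cost is a wording amendment to one appendix. Scores will no longer be directly comparable with earlier uses of the item set, which the protocol does not plan to use. Over a shorter period, more patients may choose the existing not-applicable answer to item 10, so its count should be reported.

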8.0 Study Endpoints

8.1 Study Outcomes

Primary Endpoints

Subjects will be compared with historical controls (matched for transfusion group; IPSS-R; pre-transfusion Hb; and institution) seen between 2015 and 2017. For the transfusion-naïve, the primary outcome will be receipt of second transfusion (yes/no) within 8 weeks following the index transfusion. For the transfusion-dependent, the primary outcome will be defined as number of units pRBCs received within 8 weeks following the index transfusion. For both groups, we will also compare the number of hospitalizations and clinic visits during the 8 weeks after index transfusion (Table).

Secondary Endpoints

Secondary endpoints include decisional regret, perceptions of care, and perceived stress by the associated scales at two months post-transfusion (Table 1).

Table. Primary and Secondary Outcomes, Measured at Two Months after PTQA

Primary	Presence of second transfusion after PTQA (for those undergoing first transfusion) Number of red cell units used since PTQA (for transfusion-dependent) Number of hospitalizations since PTQA Number of clinic visits since PTQA
Secondary	Decisional Regret Decision Regret Scale. ³² 5-item scale provides indicator of health care decision regret; will be tailored to measure regret about transfusion decisions. Perceptions of Care “About Your Care” Domain of Prior DFCI Survey. We previously developed ³³ a 6-item domain based on the Consumer Assessment of Healthcare Providers and Systems Survey “health status” “access,” and “communication” domains. ³⁴ Perceived Stress PSS-4. ³⁵⁻³⁷ The PSS-4 was designed for use with patients with at least a junior high school education, and takes 3 minutes to complete. It contains four questions about feelings of control and overall stress, with simple response alternatives.

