37	...were you afraid that your MDS treatment would stop working? (check here if not applicable because you are not currently being treated)					
38	...have you been too tired to take care of a family member or loved one? (check here if not applicable because you are not providing such care)					

[figure not shown]

PROTOCOL TITLE: A New Paradigm of Transfusion Decision Support for Patients with MDS:
Using Peri-Transfusion Quality of Life Assessments (PTQAs)

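### Item 11 of the follow-up survey asks for a rating of the chemotherapy or hormonal therapy prescriber, with no not-applicable option, in a study where no participant needs to be on such therapy

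*Protocol*

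**What the plan says.** Protocol Section 8.1 states: "Secondary endpoints include decisional regret, perceptions of care, and perceived stress by the associated scales at two months post-transfusion". Its table describes the perceptions-of-care instrument as a "6-item domain based on the Consumer Assessment of Healthcare Providers and Systems Survey", taken from an earlier survey at the lead institution. In Appendix E this is the block on cancer care, items 9 to 14.

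Item 11 of that block asks, from 0 to 10, "what number would you use to rate the doctor who prescribes your chemotherapy or hormonal therapy". No not-applicable response is printed. Item 10, just above it, does have one: "5 Not applicable, never needed care right away". Item 14 asks: "Which statement best describes the role you would prefer to play when decisions about treatment for your cancer are made".

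The inclusion criteria in Section 3.2 ask for adults with MDS who are either approaching transfusion or transfusion-dependent. None asks for chemotherapy or hormonal therapy. Section 22.2 gives the source population as MDS patients presenting for transfusion.

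On analysis, Section 11.1 plans "Exploratory analyses (e.g. descriptive statistics such as means and standard deviations) using the results from the follow-up survey". It states no scoring rule for the six items and no test.

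**The concern.** The item names a doctor whom some participants may not have. The block's origin explains how this could happen: the title of the paper cited for the prior survey says that it studied patients under active cancer treatment, for whom the question would fit. Here the treatment that defines the study is red cell transfusion.

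The wording of a mailed paper survey fixes what can be learned from it. A statistical analysis plan can decide how to code a response, but it cannot recover which doctor a participant had in mind. If the wording stays, one of the two 0 to 10 ratings in the block will describe a mixture of doctors. The block also has no rating aimed at the doctor with whom transfusion decisions are made, which is the relationship that the PTQA report is meant to inform.

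**Working it through.** The plan states no figure for this endpoint, so there is nothing to reproduce. The check sets the sections side by side.

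1. **Does the plan ensure that item 11 applies to everyone?** No. No criterion in Section 3.2 requires chemotherapy or hormonal therapy. Section 2.1 treats red cell transfusion as a central part of MDS care in its own right.

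2. **Does the protocol foresee participants without treatment?** Its main instrument does. QUALMS item 37 (Appendix B) has the box "check here if not applicable because you are not currently being treated". This shows that the situation is expected in MDS. It does not show how common it is in this study.

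3. **What can a participant without such therapy do with item 11?**
   - Leave it blank. The survey's instruction and Section 24 offer skipping for questions that cause discomfort, so a blank for not applicable and a blank for declined look the same.
   - Rate another doctor. That rating looks the same as one for a prescriber.

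4. **Can the cases be separated later?** Let *a* be the number who rate a prescriber, with mean *m*₁, and *b* the number who rate another doctor, with mean *m*₂. The observed mean is (*a m*₁ + *b m*₂)/(*a* + *b*). Only *a* + *b* is recorded, so neither *m*₁ nor *m*₂ can be estimated. The record review listed in Section 9.4 covers sociodemographic data, the MDS diagnosis, prior transfusions and hemoglobin; it does not name chemotherapy or hormonal therapy. QUALMS item 37 helps little. It concerns any MDS treatment at the time of the questionnaire, whereas the block in Appendix E looks back twelve months.

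5. **How many participants?** The documents do not say. If a share *p* of the 60 evaluable participants has no such therapy, and all return the survey, the number is 60*p*:

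| Assumed *p* | Participants without an answerable item 11 |
|---|---|
| 10% | 0.10 × 60 = 6 |
| 30% | 0.30 × 60 = 18 |
| 50% | 0.50 × 60 = 30 |

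6. **Item 14.** Section 8.1 says that the domain draws on health status, access and communication. Item 14 asks what role the patient would like to have in decisions. Its codes run from 1 (patient decides) to 5 (doctor decides), and neither end is better care. As an illustration only: if the six raw codes were averaged, a move from 1 to 5 on item 14 would shift a patient's score by (5 − 1)/6 = 0.67 points with no change in the care received. The protocol does not state that they will be averaged.

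**The case against.** The strongest reply is that little depends on this item. The endpoint is secondary and descriptive, with no test and no comparison with controls. Item 11 is sound for every participant who does receive such therapy, the share who do not is unknown, and blanks are permitted. This stands, and it limits the weight of the point. It does not remove the ambiguity, because a participant who answers about another doctor leaves no trace.

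A second reply is that the survey covers the transfusion conversation elsewhere. Items 1 to 3 ask whether the PTQA report was discussed and used, items 4 to 8 measure regret about the transfusion decision, and items 10, 12 and 13 ask about cancer doctors and other cancer providers. This is also fair: the interaction is covered. What is missing is only a rating aimed at that doctor.

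A reader might go further and infer that half of the block is faulty, counting items 10, 11 and 14, and that the planned means will therefore mislead. The documents do not support this:

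- Item 10 asks how promptly urgent concerns were addressed. That is access to care, one of the areas the domain is said to cover. Its response 5 is a printed label, and nothing says that it will be averaged. Setting it to missing is routine data handling, which a protocol commonly leaves to the analysis plan.
- Section 11.1 names means and standard deviations only as an example. It prescribes neither a combined score nor a mean of item 14, and a frequency table for item 14 is compatible with it as written.

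**Conclusion.** The point holds for item 11. Its wording does not fit participants without chemotherapy or hormonal therapy, it gives them no way to say so, and the resulting answers cannot be sorted out afterwards from the data the protocol lists. It affects one of six items in one secondary endpoint. The number of participants is unknown: the range of 6 to 30 of 60 rests on assumed shares of 10% to 50% and on full return of the survey.

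Item 14 is a minor accompanying point. It records a preference and does not describe care received, so it should not enter a perceptions-of-care score.

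This is a worthwhile and inexpensive improvement. No main conclusion of the study depends on it, and it gives no ground for calling the planned summaries of the whole domain misleading.

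**What to change.** Make one of two changes to item 11 in Appendix E:

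- **Reword it** to ask about the doctor with whom the patient makes decisions about transfusion. Participants can then answer whether or not they have chemotherapy or hormonal therapy, and the rating is aimed at the relationship the study is about. The cost is that the item is no longer identical to the prior survey. The protocol plans no comparison with that survey's results, so the loss is small.
- **Add a not-applicable box** and keep the wording. This separates not applicable from declined and stays closer to the prior survey, but those who tick the box still rate no doctor on this scale.

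Report item 14 as frequencies, apart from any perceptions-of-care score. This needs one sentence and no change to the survey.

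Either change to item 11 is one line on the form, with the usual approval of a revised survey. If some surveys have already been returned, record which version each participant received and report the two versions of item 11 separately.
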